7.5.6 Clinical Laboratory Findings

Laboratory data will be summarized at baseline and at each visit, as well as changes from baseline in laboratory parameters. For each summary the N, mean, median, SD, minimum, and maximum values will be given by treatment group. Pretreatment laboratory values obtained closest in time to first dose of study drug will be used for summarization of baseline and change from baseline. Clinical laboratory tests performed during the study will be analyzed by a local clinical laboratory. To standardize the laboratory reference values the normal laboratory values listed in the Merck Manual will be used.

- Serum ammonia levels
- Comprehensive Metabolic/Liver Panel (including ALT, AST, ALP, AFP, DBil, TBil, ProTime, INR; total serum protein)
- Hematology: CBC w/Differential
- Alpha fetoprotein (AFP) only in lieu of recent HCC imaging at screening only
- Serum pregnancy test. NOTE: Serum pregnancy tests performed upon hospital admission, prior to study consent, may be used at Screening.
- Urinalysis
- Urine pregnancy test

7.5.7 Vital Signs Measurements

Vital signs will be summarized at baseline and at each visit, as well as changes from baseline in vital sign measurements. For each summary the N, mean, median, SD, minimum, and maximum values will be given by treatment group. Pretreatment vital signs obtained closest in time to first dose of study drug will be used for summarization and analysis of baseline and change from baseline vital signs.

Vital signs will include supine blood pressure (mmHg), heart rate (beats per minute), respiratory rate, weight and temperature. Height (cm) will be collected at Screening only.

Vital sign measurements will be collected at every visit. Supine blood pressure measurements should be measured on the same arm throughout the study.

7.6 Interim Analysis

An interim analysis will be conducted when at least 10 subjects per treatment group have completed participation in the blinded treatment period of the study. The CRO/Sponsor designee will remain blinded, whereas a few designated members of the Sponsor's team who do not have direct involvement with the ongoing study will be unblinded at the interim analysis stage. The interim results will not be shared outside of the small designated team, and no changes will be made to the ongoing study based on the interim study results.

8.0 STUDY METHODS

8.1 Study Visits

Following identification of a potential subject, the Investigator (or designee) will explain the purpose of the study, procedures, risks/benefits, and subject responsibilities to the potential subject's caregiver. The subject's ability to meet the requirements of the study will be determined in discussions with the caregiver. If the caregiver consents on behalf

Clinical Study Protocol, Amendment 3, dated 08 January 2020

CONFIDENTIAL

Page 38

of the subject the person obtaining written consent will sign and date the IRB/EC-approved ICF, at which point the subject is considered part of the study population. The original signed document will be retained in the subject records, and a copy will be provided to the subject/caregiver. In addition, the applicable privacy regulation requirements must be met.

Study Visit procedures are outlined in [Table 1](#).

Table 1: Study Design and Schedule of Assessments

	Blinded Randomized Treatment Period		Hospital Discharge	Open-label Safety Follow-up Period		
	Screening & Baseline	Treatment Period		Follow-up ⁴ Visit 1	Follow-up ⁴ Visit 2	Follow-up ⁴ Visit 3/ EOS ⁸
Study Day	Study Day 1	Study Day 2 Up to Study Day 15		Day 7 Post Resolution (±2)	Day 14 Post Resolution (±2)	Day 30 Post Resolution (±2)
Informed Consent	X					
Review inclusion / exclusion criteria	X					
Medical History and Demographics	X					
Record Concomitant Medications	X	X	X	X	X	X
Discontinue use of prohibited medications	X					
Vital Signs and Weight (kg)	X	X		X	X	X
Height (cm)	X					
Physical Examination	X	X ²		X	X	X
Clinical Laboratory Tests/ Urinalysis	X ⁵	X		X	X	X
Serum/Urine Pregnancy Test	X ⁶					X ⁶
HEGI ¹	X	X ²		X	X	X
WHC ¹	X	X ²		X	X	X
CBI ¹	X			X	X	X
Randomize Subject in EDC	X					
Dispense/Administer 1 st Dose of Blinded Study Drug		X ²				
Record dates/times of study drug dosing		X				
Record Bristol Stool Appearance		X				
Record lactulose use (dosing time and amount) dates/times of lactulose use	X	X		X ³	X ³	X ³
Assess Open-Label Dosing Compliance				X ³	X ³	X ³
Record Adverse Events	X	X	X	X	X	X
Dispense Open Label Xifaxan® 550mg and Review Dosing Instructions			X ⁷			
CLDQ ¹				X	X	X

Abbreviations: EOS = end of study

All Subject assessments will be performed by a trained and qualified Evaluator. Efforts should be made to have the same evaluator assess the same Subject for as many HEGI assessments as possible. Every effort must be made for the same Evaluator to conduct the HEGI assessments at both the resolution of OHE and the confirmation of resolution assessed 3 to 12 hours later.

¹Evaluator, defined by only licensed physicians, physician's assistants or nurse practitioners, who are trained in these instruments may conduct the assessment.

²Assessments are conducted twice per day, approximately 12 hours (±2 hours) apart. Following resolution of OHE, a confirmatory HEGI (3 to 12 hours post initial resolution) must be done to complete the blinded randomized treatment phase.. Subjects should continue to dose on blinded study medication until OHE resolution is confirmed.

³Subject will report on lactulose use (if any) and open-label dosing compliance from previous visit to current visit. Diary cards are not being used on this study.

⁴Open-label Safety Follow-up visits will be conducted by a study investigator.

⁵Clinical laboratory tests run within 24 hours of consent, may be used in place of drawing new labs at Screening provided all protocol required labs are present. Note: AFP is only required at Screening.

⁶ Serum pregnancy test is done at Screening and urine pregnancy test at EOS visit (open-label safety follow-up Visit 3)

⁷ Open-label drug should only be dispensed to subjects upon hospital discharge. Please note this may be on a different day than OHE resolution.

⁸ If a subject early terminates/discontinues during the study, the visit schedule at the end of the that treatment phase should be followed for their ET visit.

8.1.1 Day 1: Screening / Baseline

The following procedures are to be completed at the Screening/Baseline visit, prior to randomization:

- Informed consent is to be signed by the subject's caregiver prior to performing any study evaluations or procedures, including discontinuing any prohibited medications.
- Allocate subject screening identification number to eligible subjects in ascending order using the next available consecutive number on the list.
- Review Inclusion/Exclusion criteria to ensure subject qualifies for the study.
- Conduct serum pregnancy test (for female subjects of childbearing potential) and confirm that it is negative. Note: Serum pregnancy tests performed upon hospital admission, prior to study consent, may be used at Screening.
- Complete a full physical examination, including evaluation for complications of liver cirrhosis.
- Collect demographic information, significant medical history, and hospital admission data including diagnosis of liver cirrhosis and OHE and HEGI grade.
- Collect vital sign measurements (include weight, height, supine blood pressure, heart rate, respiration rate and temperature). Height will only be collected at Screening.
- Record all concomitant medications administered within the 30 days prior to screening visit, and ensure that all prohibited medications are discontinued
- Collect blood and urine for clinical laboratory tests (hematology, blood chemistry, and urinalysis). Labs drawn within 24 hours of consent may be used at Screening provided all protocol required labs are present.
- Subject must have a Grade 2 or Grade 3 HEGI score ([Appendix A](#)) following lactulose treatment and adequate hydration (IV fluids at PI discretion). NOTE: Duration of hospital admission prior to enrollment is not restricted provided the hydration and lactulose treatment occurred within a reasonable timeframe to subject randomization.
- Determine and record WHC score. ([Appendix B](#))
- Assess Caregiver Burden Index ([CBI; Appendix C](#)).

After all Screening/Baseline procedures have been completed and necessary information has been collected:

- Randomize subject onto study using a randomization code obtained from the IRT.
- Record date, time(s) and dose(s) of lactulose.
- Record all AEs.

8.1.2 Day 2 up to Day 15: Randomized Treatment Period

The following are to be conducted each day the subject is hospitalized.

Conducted Daily

- Record all concomitant medications and AEs.
- Collect vital sign measurements (include weight, supine blood pressure, heart rate, respiration rate and temperature).
- Collect blood and urine for clinical laboratory tests (hematology, blood chemistry, and urinalysis).
- Dispense study drug and administer dose to subject.
- Record date and times of study drug dose.
- Record date, time(s) and dose(s) of lactulose.
- Record frequency of bowel movements and stool appearance. ([Bristol, Appendix E](#))

Conducted TWICE Daily at 12 Hour (± 2 Hr) Intervals (approx. 7AM and 7PM)

- Complete a full physical examination, including evaluation for complications of liver cirrhosis.
- Determine and record HEGI score. ([Appendix A](#))
- Determine and record WHC score. ([Appendix B](#))

Criteria for OHE Resolution

For the purposes of this clinical study, OHE resolution is determined solely on the HEGI score. A HEGI score of < 2 indicates resolution of OHE, whereas a HEGI score of ≥ 2 indicates a continuation of the OHE episode.

Resolution of the OHE episode (HEGI score of < 2) must be confirmed by a repeat evaluation (HEGI) at least 3 and no more than 12 hours after the initial evaluation to demonstrate persistence of the OHE resolution.

- If the OHE resolution is not confirmed by this repeat evaluation, the subject continues in the study until OHE resolution occurs again and is subsequently confirmed by a repeat evaluation 3-12 hours following.
- If the OHE resolution is confirmed by this repeat evaluation, the subject is considered resolved. Resolution of OHE will be recorded as the date/time of the HEGI assessment immediately prior to the confirmation evaluation. NOTE: Subjects should continue to dose on blinded study medication until OHE resolution is confirmed.

8.1.3 OHE Resolution

The following procedures will occur upon OHE resolution with confirmatory HEGI.

- Record all concomitant medications and AEs.

Clinical Study Protocol, Amendment 3, dated 08 January 2020

CONFIDENTIAL

Page 42

- Collect vital sign measurements (include weight, supine blood pressure, heart rate, respiration rate, and temperature).
- Complete a full physical examination, including evaluation for complications of liver cirrhosis.
- Collect blood and urine for clinical laboratory tests (hematology, blood chemistry, and urinalysis).
- Determine and record HEGI score. ([Appendix A](#))
- Determine and record WHC score. ([Appendix B](#))
- Dispense Xifaxan® 550mg (BID dosing) and review dosing instructions with subject.
- Schedule and review the open-label safety follow-up visits with subject.
- Record stool appearance. ([Bristol, Appendix E](#))

If the subject discontinues or early terminates from the study prior to starting the open-label safety follow-up period, the OHE Resolution visit assessments are to be done as the subjects early termination/discontinuation visit and the subject exited from study. Please refer to [Section 8.3.1](#) for a list of early termination/discontinuation procedures to be conducted.

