- **Normal Study Completion** – subject completes study as planned per the protocol
- **Adverse Event** – complete AE form

- **Subject Request** – consent withdrawal (i.e. subject moved, schedule conflicts)
- **Protocol Violation** – contact the Sponsor or Sponsor's designee prior to making decision
- **Lost to Follow-Up** – document with two phone calls and a certified letter
- **Pregnancy** – subject will discontinue study drug immediately, but will be followed to term; pregnancy form must be completed
- **Worsening Condition** – subject requires alternate treatment prior to completing the study and the investigator determines it is not due to lack of efficacy (i.e. requires liver transplant during the study).
- **Other** – specify in the comments section of final eCRF

Subjects who terminate treatment early will be asked to complete all end of study visit assessments (see [Section 8.3.1](#) for additional information) prior to commencement of any alternative medication or therapy (if possible). Subjects who discontinue from the study during the treatment period will be asked to come back for the 30 day post-treatment cessation follow-up visit.

All subjects are free to withdraw from participating in this study at any time and for whatever reason, specified or unspecified, and without prejudice. No constraints will be placed on ordinary subject management, and subjects, when appropriate, will be placed on other conventional therapy upon request or whenever clinically necessary as determined by their physician.

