7.4 Study Populations

Intent to Treat (ITT): The ITT population will include all randomized subjects who received at least one dose of study drug.

Analysis on the ITT sample will be used as the primary efficacy analysis and will be performed for all efficacy endpoints. Subjects will be analyzed in the treatment group to which they were randomized.

Per Protocol (PP): The PP population will include all ITT subjects who remain in the study through the end of the blinded randomized treatment period and who have not deviated from the protocol in any way likely to seriously affect the primary outcome of the study. Important protocol deviations will be identified prior to locking the study database.

Safety: The safety population will include all subjects who received at least 1 dose of study drug. All subjects in the safety population will be analyzed according to the treatment they actually received.

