8.3.1 Early Study Termination

If the subject discontinues or early terminates from the study during the blinded treatment period, the following assessments are to be collected:

- All concomitant medications and AEs.
- Vital sign measurements (include weight, supine blood pressure, heart rate, respiration rate, and temperature).

- Complete physical examination, including evaluation for complications of liver cirrhosis.
- Blood and urine for clinical laboratory tests (hematology, blood chemistry, and urinalysis).
- HEGI score. ([Appendix A](#))
- WHC score. ([Appendix B](#))

If the subject discontinues or early terminates from the study during the open-label safety follow-up period, the following visit assessments are to be collected:

- All concomitant medications and AEs.
- Vital sign measurements (include weight, supine blood pressure, heart rate, respiration rate and temperature).
- Complete physical examination, including evaluation for complications of liver cirrhosis.
- Blood and urine for clinical laboratory tests (hematology, blood chemistry, and urinalysis).
- Record date, time(s) and dose(s) of lactulose, if taken.
- HEGI score. ([Appendix A](#))
- WHC score. ([Appendix B](#))
- Assess health outcomes indices via CBI ([Appendix C](#)) and CLDQ ([Appendix D](#)).
- Urine pregnancy test.

If during the study it becomes evident to the Sponsor that the study should be stopped prematurely, the study will be terminated and appropriate notification will be given to the Investigators, IRB, and FDA, as applicable. The Sponsor will instruct the Investigators to stop dispensing study materials/treatment and to arrange for study closeout at each site.

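### The protocol does not separate stopping blinded drug from leaving the study, and provides no HEGI scoring to Day 15 after discontinuation for subjects whom the ITT analysis keeps

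*Combined protocol and SAP*

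**What the plan says.** The withdrawal text in Section 5.2.1.2 (Subject Withdrawal Criteria) starts from treatment: "Subjects who terminate treatment early will be asked to complete all end of study visit assessments". It refers to Section 8.3.1 for detail, but that section has a different trigger: "If the subject discontinues or early terminates from the study during the blinded treatment period, the following assessments are to be collected". The list that follows holds one HEGI and one WHC, with no repeat.

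Section 8.1.3 uses the same trigger, "If the subject discontinues or early terminates from the study prior to starting the open-label safety follow-up period", and gives the consequence: "the OHE Resolution visit assessments are to be done as the subjects early termination/discontinuation visit and the subject exited from study". Section 5.2.1.2 nevertheless asks for a later contact: "Subjects who discontinue from the study during the treatment period will be asked to come back for the 30 day post-treatment cessation follow-up visit".

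During blinded treatment, Section 8.1.2 requires HEGI and WHC twice daily and introduces its procedures with "The following are to be conducted each day the subject is hospitalized". A resolution counts only if a second HEGI, 3 to 12 hours later, confirms it (Sections 7.1, 7.5.4 and 8.1.2).

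Section 7.4 puts every randomized subject with at least one dose in the ITT population and adds: "Analysis on the ITT sample will be used as the primary efficacy analysis and will be performed for all efficacy endpoints". The only censoring rule, in Section 7.5.4, covers subjects who complete 14 days unresolved.

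**The concern.** A subject who stops blinded tablets on, say, day 3 may still be in hospital, with overt HE that trained evaluators could go on scoring. Read together, the sections route that subject to one termination visit and then out of the study. Even a score below 2 at that visit could not become an event, because no confirmation is listed. The subject stays in the primary analysis with an outcome cut off at discontinuation.

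Subjects who stop for worsening, adverse events or inability to take tablets are plausibly slower resolvers. If they stop more often in one arm and are censored at exit, the subjects left at risk in that arm look better than those randomized to it. Scores that were not taken can be bounded later but not recovered.

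**Working it through.** **1. Is there a path for stopping drug and staying in?**

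| Place | Trigger | What follows |
|---|---|---|
| 5.2.1.2 | Ends treatment early | End-of-study assessments; refers to 8.3.1 |
| 8.3.1 | Leaves the study in the blinded period | One set, with a single HEGI |
| 8.1.3 | Leaves the study before open-label treatment | One visit, then exit |
| 5.2.1.2 | Leaves the study in the treatment period | Return visit 30 days after treatment ends |
| 8.1.2 | Each hospital day, under the treatment-period heading | Twice-daily HEGI and WHC |
| 8.6 | Protocol deviation | Assessments continue |

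No row clearly keeps a subject who has stopped drug in twice-daily scoring. The 30-day visit falls after the endpoint window and conflicts with exit in 8.1.3.

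**2. The plan's own sample size.** Section 7.3 gives 61 evaluable per group for 76% versus 51%, two-sided 0.05, 80% power. The Freedman formula reproduces it if the two percentages are entered as event-free: HR = ln 0.76 / ln 0.51 = 0.408; events = (1.96 + 0.84)² × (1.408/0.592)² = 44.3; n = 44.3 / (2 − 0.76 − 0.51) = 60.7, so 61. Read as resolution rates, as the text has them, HR = ln 0.24 / ln 0.49 = 2.00, and power at 61 per arm is 86.3% (Schoenfeld) or 83.5% (Freedman). The stated power is not in doubt.

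**3. Power.** With 65 per arm, expected events per comparison are 65 × (0.76 + 0.51) = 82.6. The share lost to early exit is assumed.

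| Events lost | Schoenfeld | Freedman |
|---|---|---|
| 0% | 88.3% | 85.8% |
| 10% | 84.8% | 82.0% |
| 20% | 80.4% | 77.3% |

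In a simulation with equal stopping and 12-hourly visits, power is 89% with no exits. With a 20% 14-day risk of stopping it is 85% if exits are censored and 82% if they are held unresolved to Day 14. The loss is moderate.

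**4. Bias with no drug effect.** Assumptions: 65 per arm; usual daily hazard −ln(0.49)/14 = 0.051; slow resolvers equally common in both arms, since randomization balances them; only slow resolvers stop, on days 1 to 5; exits censored. The true HR is 1.00. An HR above 1 favours the arm with more stopping.

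- *Mild:* 10% of subjects resolve at half the usual hazard; all of them stop in one arm and half in the other (10% versus 5% of the arm). Hand check: after the stops, the first arm has mean relative hazard 1. The second has (0.90 + 0.05 × 0.5)/0.95 = 0.974, and 1/0.974 = 1.03. Simulated over the whole window, the HR is about 1.02, with no inflation of rejection.
- *Extreme:* 20% resolve at a quarter of the usual hazard; all stop in one arm and a quarter in the other (20% versus 5%). Hand check: (0.80 + 0.05 × 3 × 0.25)/0.95 = 0.882, and 1/0.882 = 1.13. The simulated HR is 1.12 to 1.13, with rejection of about 7% to 8% against a nominal 5%. With the arms exchanged, the HR is about 1/1.13 = 0.88.

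Holding exits as unresolved to Day 14 in the extreme case gives HR 0.94 and 5.8% rejection, so the two simple rules fall on either side of the truth.

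A harsher model, in which only subjects who would not have resolved by Day 14 exit and are censored, gives rejection of about 8% (10% versus 40% of them exit) and 10% (20% versus 60%).

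**The case against.** The strongest reply is that Section 8.1.3 does not say that stopping drug ends participation; its trigger is leaving the study. Section 8.1.2 ties scoring to being in hospital, Section 8.6 continues assessments after deviations, and Section 7.5.5 reports treatment discontinuation apart from study withdrawal. A site could read these as keeping the subject in. This stands in part. A reader might infer a rule that every drug stop means exit, or that the outcome is never observed after a stop. The documents support neither: the link is an inference from 5.2.1.2 and 8.3.1, and one HEGI is taken at termination. But 8.1.2 sits under the treatment-period heading and 8.6 concerns deviations, so nothing settles the matter. If sites differ in their reading, collection will differ by site.

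A reader might also infer that lack of efficacy and death cannot be told from administrative exits, because *Worsening Condition* applies only where "the investigator determines it is not due to lack of efficacy" and no separate code exists for either. That does not follow. Section 7.5.5 tabulates TEAEs with a fatal outcome and lists all deaths, and *Other* requires the reason to be specified.

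Two further points stand. The bias is material only under strong assumptions, and sensitivity analyses can bound much of it. Scores taken after a stop may also reflect other therapy, so using them in the primary analysis is an estimand choice that should be stated.

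**Conclusion.** The point holds as a gap in outcome collection. The protocol does not distinguish drug discontinuation from study withdrawal and provides no scoring, with confirmation, to Day 15 for a subject who has stopped drug, although the primary analysis retains that subject. The exit rule also conflicts with the 30-day return visit.

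The main risk is informative censoring, not power. If exits are censored, the null hazard ratio moves to about 1.02 in the mild case and about 1.13, with 7% to 8% rejection, in the extreme one. These figures rest on assumed stopping rates and slow-resolver shares, since the documents give none. They do not show that the trial will be biased. They show that the result could depend on outcomes the protocol does not provide for recording. An amendment is worthwhile because collection is cheap and cannot be done afterwards.

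**What to change.** Amend Sections 5.2.1.2, 8.1.3 and 8.3.1:

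- Define discontinuation of blinded drug and withdrawal from the study separately.
- For a subject off blinded drug who remains hospitalized and has not withdrawn consent, continue the scheduled twice-daily HEGI and WHC, with the 3 to 12 hour confirmation, until confirmed resolution, Day 15, discharge or death.
- Use these scores in the ITT analysis, and record any alternative HE therapy started and when.
- Specify two sensitivity analyses: censoring at drug stop, and holding the subject unresolved to Day 14.
- Reconcile exit in 8.1.3 with the 30-day return visit in 5.2.1.2.

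The cost is a short amendment, a CRF edit and a few more bedside scores by evaluators already in place. The drawback is that some scores after the stop may reflect other therapy; the therapy record and the sensitivity analyses are there to show how far that matters. No treatment rule changes.
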